10.2 Study Hypotheses Tested

For the primary analyses of treatment efficacy, let p_{RC} be the proportion with partial or greater response in hemangioma volume for the control cohort, p_{R25} the proportion with partial or greater response in hemangioma volume for the 0.25% arm, and p_{R50} the proportion with partial or greater response in hemangioma volume for the 0.5% arm. The following set of hypotheses will be assessed:

Hypothesis 1 (H_1): The partial response proportion in the 0.5% arm is greater than the partial response proportion in the control cohort.

Null hypothesis H_{10} : $p_{R50} \leq p_{RC}$

Alternative hypothesis H_{1A} : $p_{R50} > p_{RC}$

Hypothesis 2 (H_2): The partial response proportion in the 0.25% arm is greater than the partial response proportion in the control cohort.

Null hypothesis H_{20} : $p_{R25} \leq p_{RC}$

Alternative hypothesis H_{2A} : $p_{R25} > p_{RC}$

A secondary efficacy hypothesis comparing treatment arms will also be tested:

Secondary efficacy hypothesis (H_3): The partial response proportion in the 0.25% arm is not equal to the partial response proportion in the 0.5% arm.

Null hypothesis H_{30} : $p_{R25} = p_{R50}$

Alternative hypothesis H_{3A} : $p_{R25} \neq p_{R50}$

The $\alpha=0.05$ level will be used for hypothesis testing. Hypotheses will be tested with chi-square or Fisher's exact tests. A Bonferroni multiplicity correction will be applied to the α level for the primary hypotheses. Response proportions will be further compared between groups using the odds ratio or estimated differences in proportions and corresponding confidence interval estimates.

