10.3 Sample Size Considerations

Sample size calculations for primary efficacy hypotheses assume that 35 participants will have evaluable data in the untreated control cohort. The following success rates are assumed: 0.15 response proportion in the control cohort, 0.45 response proportion in the 0.25% arm, and 0.50 response proportion in the 0.5% arm. With 45 participants in each treatment arm and $\alpha = 0.05$ as in Section 10.2, this gives the efficacy hypothesis comparing the 0.5% and control arms a power of 93% and the efficacy hypothesis comparing the 0.25% and control arms a power of 85% after applying the Bonferroni multiplicity correction to the alpha level. The study sample size of 100 randomized participants was determined by assuming that up to 10% of randomized infants will drop out with unevaluable partial response.

Sample size calculations for the secondary safety analyses assume that approximately 20% of participants will experience an AE of special interest and 5% will experience an SAE of special interest.^{24,32} With 100 participants across the two treatment groups, 95% Wilson score confidence intervals are (0.02,0.11) (confidence interval width=0.09) for SAEs and (0.13,0.29) (confidence interval width=0.16) for AEs. These intervals are thought to be sufficiently precise for the estimation of key event rates. The probability is 0.63 and 0.99 that at least one event will be seen in the study population for rare events with probabilities 0.01 and 0.05, respectively, of occurring.

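### Plain Bonferroni on the two primary comparisons gives up about 6 points of power for the 0.25% arm, and 7 to 9 points for both arms succeeding, that Holm's procedure recovers at the same family-wise error rate

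*Combined protocol and SAP*

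**What the plan says.** Section 10.2 of the combined protocol and SAP sets two directional primary hypotheses against the same control cohort:

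- H1: "The partial response proportion in the 0.5% arm is greater than the partial response proportion in the control cohort"
- H2: "The partial response proportion in the 0.25% arm is greater than the partial response proportion in the control cohort"

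Overall alpha is 0.05. For the method it says "Hypotheses will be tested with chi-square or Fisher's exact tests", and for multiplicity "A Bonferroni multiplicity correction will be applied to the" alpha used for the primary hypotheses. With two hypotheses that is 0.05/2 = 0.025 each.

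Section 10.3 reports 93% power for the 0.5% arm and 85% for the 0.25% arm "after applying the Bonferroni multiplicity correction to the alpha level". Neither section describes a step-down, gatekeeping or alpha-recycling rule. Neither gives the probability that both comparisons succeed.

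**The concern.** Under plain Bonferroni, each hypothesis stays at 0.025 even after the other has been rejected. At that point only one primary hypothesis can still be falsely rejected, and the whole 0.05 could be spent on it. Holm's procedure does this. It needs no ranking of the two strengths, which suits Section 10.2 because none is given there.

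The 0.25% comparison is the weaker one, and the primary objective in Section 3 covers both strengths. Unused alpha therefore falls mainly on the chance of showing efficacy for the lower strength, and on the chance of showing it for both. The control cohort comes mainly from photographs of completed trials (Section 4.1.1), so it cannot easily be enlarged to regain that power.

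**Working it through.** **Inputs (Sections 10.2 and 10.3).** Control response 0.15 with n = 35; 0.25% arm 0.45 with n = 45; 0.5% arm 0.50 with n = 45; overall alpha 0.05; two primary hypotheses; directional alternatives.

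**Step 1: reproduce the stated power.** Pooled normal approximation at one-sided 0.025 (critical value 1.960):

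power = Φ[(d − 1.960·SE0)/SE1], where SE0 uses the pooled proportion and SE1 the separate proportions.

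- 0.25% arm: d = 0.30; pooled proportion (5.25 + 20.25)/80 = 0.3188; SE0 = 0.1050; SE1 = √(0.1275/35 + 0.2475/45) = 0.0956. Power = Φ(0.985) = 83.8%.
- 0.5% arm: d = 0.35; pooled proportion (5.25 + 22.5)/80 = 0.3469; SE0 = 0.1073; SE1 = √(0.1275/35 + 0.25/45) = 0.0959. Power = Φ(1.457) = 92.7%.

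The arcsine approximation gives 85.0% and 93.1%. Exact binomial enumeration of the chi-square test gives 84.3% and 92.9%. The plan's 85% and 93% are therefore reproduced at one-sided 0.025 per comparison. Two-sided 0.025 does not reproduce them (pooled 75.0% and 87.3%). Uncorrected two-sided 0.05 has the same critical value, so the power figures alone cannot separate it from one-sided 0.025. The directional hypotheses and the stated correction point to one-sided 0.025.

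**Step 2: Bonferroni against Holm, exactly.** For each control count c with probability w(c), let L be the conditional probability that an arm's p-value is at most 0.025, and M the same for 0.05. Given c, the two arms are independent.

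- 0.25% arm, Bonferroni: Σ w·L25. Holm: Σ w·[L25 + (M25 − L25)·L50].
- Both arms, Bonferroni: Σ w·L25·L50. Holm: Σ w·[L25·L50 + (M25 − L25)·L50 + (M50 − L50)·L25].

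| Chi-square, exact | Bonferroni | Holm | Gain (points) |
|---|---|---|---|
| One-sided: 0.25% arm | 84.3% | 89.9% | 5.5 |
| One-sided: 0.5% arm | 92.9% | 94.9% | 2.0 |
| One-sided: both arms | 80.8% | 88.3% | 7.5 |
| One-sided: at least one | 96.5% | 96.5% | 0 |
| Two-sided: 0.25% arm | 76.2% | 82.6% | 6.4 |
| Two-sided: 0.5% arm | 87.9% | 90.4% | 2.5 |
| Two-sided: both arms | 71.1% | 80.0% | 8.9 |

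Gains are taken before rounding.

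**Step 3: other tests, one-sided.** Fisher's exact test: 0.25% arm 78.8% to 85.2% (+6.4), both arms 74.1% to 82.9% (+8.8). Bivariate normal with correlation 0.397 from the shared control, (0.1275/35)/(0.0956 × 0.0959): 0.25% arm 83.8% to 89.9% (+6.1), both arms 79.4% to 87.9% (+8.5).

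**Step 4: type I error, one-sided chi-square, control rate 0.15.** With both nulls true, the family-wise error is 4.0% under either procedure, because Holm's first step is Bonferroni. With only the 0.25% null true and the 0.5% arm at 0.50, the false-positive rate for the 0.25% arm is 2.3% under Bonferroni and 4.6% under Holm. All are below 5%.

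**The case against.** **Bonferroni is valid.** Section 10.3 already budgets for it, and each comparison is powered separately; nothing requires both strengths to succeed. This stands: the point concerns efficiency, and Holm does not change the chance of at least one success. But the 0.25% comparison is itself primary, and its own power rises by 5.5 to 6.4 points one-sided.

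**The two-sided figures are not the plan's reading.** Correct. The one-sided gains of 5.5 and 7.5 points are the ones to compare with the stated 85% and 93%. The two-sided rows apply only if the chi-square tests are run two-sided.

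**Holm spends error.** When only the 0.5% arm works, the 0.25% false-positive rate doubles from 2.3% to 4.6%. This is a real trade, but it lies within the 0.05 the plan has chosen to accept.

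**The extra rejections are marginal.** They have one-sided p-values between 0.025 and 0.05, against a control group that is not randomized. Bias in that control is a serious matter, but neither procedure addresses it, and the plan does not justify Bonferroni on that ground.

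**Confidence intervals.** Bonferroni at one-sided 0.025 pairs with an ordinary two-sided 95% interval. Under Holm, an arm declared effective at one-sided 0.05 could have a 95% interval that includes no difference. This stands as a reporting point. Sections 10.2 and 10.4.4 promise no multiplicity-adjusted intervals, so no commitment is lost.

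**The gain depends on 35 controls.** Section 4.1.1 anticipates about 35 external placebo infants plus about 10 enrolled untreated ones. With 45 evaluable controls, Bonferroni gives 96.1%, 89.8% and 87.4% (0.5% arm, 0.25% arm, both), and the Holm gain falls to 4.1 points for the 0.25% arm and 5.4 for both. It is smaller but still positive.

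**Conclusion.** The concern holds. Plain Bonferroni is correct but less powerful than Holm whenever at least one strength works, at the same family-wise level. Using the plan's response rates, 35 controls and one-sided testing, Holm adds 5.5 to 6.4 points for the 0.25% arm, about 2 for the 0.5% arm and 7.5 to 8.8 for both, depending on the test. By the exact chi-square figures, the chance of missing an effective 0.25% strength falls from 15.7% to 10.1%, and of missing at least one effective strength from 19.2% to 11.7%. With controls held at 35, matching this under Bonferroni would take roughly 63 to 69 evaluable infants per treated arm instead of 45. The sizes rest on the response rates in Section 10.3; the ordering of the two procedures does not.

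**What to change.** In Section 10.2, replace the Bonferroni sentence with:

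> The two primary hypotheses will be tested with the Holm procedure: the smaller p-value is compared with alpha/2 and, if that hypothesis is rejected, the larger p-value is compared with alpha.

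Update Section 10.3 with power under Holm, including the probability that both comparisons succeed, and name the test and sidedness used. Add that the reported intervals are not multiplicity-adjusted and may not match the Holm decision.

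The cost is a short text change and recalculated power figures. No infants, visits, data or extra analyses are added. The change must be fixed before any efficacy data are seen by treatment group, because a later switch would not be credible. Section 6.6 places the central ratings at the end of the study.

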10.3 Sample Size Considerations

Sample size calculations for primary efficacy hypotheses assume that 35 participants will have evaluable data in the untreated control cohort. The following success rates are assumed: 0.15 response proportion in the control cohort, 0.45 response proportion in the 0.25% arm, and 0.50 response proportion in the 0.5% arm. With 45 participants in each treatment arm and $\alpha = 0.05$ as in Section 10.2, this gives the efficacy hypothesis comparing the 0.5% and control arms a power of 93% and the efficacy hypothesis comparing the 0.25% and control arms a power of 85% after applying the Bonferroni multiplicity correction to the alpha level. The study sample size of 100 randomized participants was determined by assuming that up to 10% of randomized infants will drop out with unevaluable partial response.

Sample size calculations for the secondary safety analyses assume that approximately 20% of participants will experience an AE of special interest and 5% will experience an SAE of special interest.^{24,32} With 100 participants across the two treatment groups, 95% Wilson score confidence intervals are (0.02,0.11) (confidence interval width=0.09) for SAEs and (0.13,0.29) (confidence interval width=0.16) for AEs. These intervals are thought to be sufficiently precise for the estimation of key event rates. The probability is 0.63 and 0.99 that at least one event will be seen in the study population for rare events with probabilities 0.01 and 0.05, respectively, of occurring.

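### Do the stated powers of 93% and 85% fail to hold after the Bonferroni correction?

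*Combined protocol and SAP*

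**What the plan says.** Section 10.2 of the combined protocol and SAP sets out three hypotheses on the proportion with at least a partial response in volume. The two primary ones are directional. H1 reads "The partial response proportion in the 0.5% arm is greater than the partial response proportion in the control cohort" and H2 reads "The partial response proportion in the 0.25% arm is greater than the partial response proportion in the control cohort"; each null is written as less than or equal to the control proportion. The secondary H3 is non-directional: "The partial response proportion in the 0.25% arm is not equal to the partial response proportion in the 0.5% arm".

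On level and method, the same section says "The $\alpha=0.05$ level will be used for hypothesis testing", then "Hypotheses will be tested with chi-square or Fisher's exact tests", then "A Bonferroni multiplicity correction will be applied to the α level for the primary hypotheses". It does not say whether the p-values are one-sided or two-sided, or when Fisher's test replaces chi-square. Section 10.4.4 names the same two tests, again without a rule.

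Section 10.3 refers back to 10.2 for alpha and, for the 0.5% and 0.25% arms in turn, reports "a power of 93% and the efficacy hypothesis comparing the 0.25% and control arms a power of 85% after applying the Bonferroni multiplicity correction".

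**The concern.** A two-sided 0.05 test with no multiplicity correction has a critical value of 1.96, and that value gives 93% and 85% almost exactly. A reader who takes a chi-square test as two-sided by default will therefore suspect that the correction is claimed but absent from the calculation. Three features of the text encourage this. The Pearson chi-square statistic has no direction, one level of 0.05 covers both the directional primary hypotheses and the two-sided H3, and nothing states the side.

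If the primary tests were run two-sided at 0.025, power for the 0.25% arm would be 76% with chi-square and 72% with Fisher, against the stated 85%. The type II error for that comparison would be 24% or 28% instead of 15%, and the sample size of 100 rests on these figures. The open choice could also affect the result: some data sets are significant under one permitted combination of test and side and not under another.

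**Working it through.** **Inputs.** Section 10.3: control n = 35, each timolol arm n = 45, response rates 0.15 (control), 0.45 (0.25% arm) and 0.50 (0.5% arm). Section 10.2: alpha 0.05, Bonferroni over two primary hypotheses, so 0.05/2 = 0.025 each. One-sided 0.025 has critical value 1.960; two-sided 0.025 has 2.241.

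**Reproducing the stated power with the arcsine formula.** Power = Φ(h/√(1/35 + 1/45) − z), where h = 2 arcsin√p_T − 2 arcsin√p_C and √(1/35 + 1/45) = 0.2254.

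- 0.5% arm: h = 1.5708 − 0.7954 = 0.7754; 0.7754/0.2254 = 3.440; 3.440 − 1.960 = 1.480; power 93.1%.
- 0.25% arm: h = 1.4706 − 0.7954 = 0.6752; 0.6752/0.2254 = 2.996; 2.996 − 1.960 = 1.036; power 85.0%.

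**Pooled normal approximation.** Power = Φ((p_T − p_C − z·SE0)/SE1), with SE0 from the pooled rate and SE1 from the separate rates.

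- 0.5% arm: pooled rate (5.25 + 22.5)/80 = 0.3469; SE0 = 0.1073; SE1 = 0.0959; (0.35 − 1.960 × 0.1073)/0.0959 = 1.457; power 92.7%.
- 0.25% arm: pooled rate (5.25 + 20.25)/80 = 0.3188; SE0 = 0.1050; SE1 = 0.0956; (0.30 − 1.960 × 0.1050)/0.0956 = 0.985; power 83.8%.

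**Exact enumeration.** All 36 × 46 outcomes are weighted by their binomial probabilities and each test is applied at 0.025.

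| Test at 0.025 | 0.5% arm vs control | 0.25% arm vs control |
|---|---|---|
| Chi-square, uncorrected, one-sided | 92.9% | 84.3% |
| Fisher, one-sided | 89.7% | 78.8% |
| Chi-square, uncorrected, two-sided | 87.9% | 76.2% |
| Fisher, two-sided | 85.4% | 71.9% |

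The first row agrees with the plan to within a point. An uncorrected two-sided 0.05 chi-square test also gives 92.9% and 84.3%, because it shares the critical value. The figures alone therefore cannot show whether the correction was applied.

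**Which row the text points to.** A null of less than or equal, set against an alternative of greater than, is the usual form of a one-sided test. Writing H3 as equal against not equal shows that the authors kept the two forms apart. This leaves the first two rows.

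**Chi-square or Fisher.** At the planned rates the smallest expected count is 35 × 0.3188 = 11.2 for the 0.25% comparison and 35 × 0.3469 = 12.1 for the 0.5% comparison. For an expected count below 5, the usual trigger for Fisher, the pooled rate would have to fall below 5/35 = 0.143. That means 11 or fewer responders among 80, where 25.5 and 27.75 are planned. Chi-square is the test to expect, which leaves the first row.

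**The case for a change.** The strongest reply is that a power statement should follow from the plan without the reader having to choose. Software usually prints a two-sided p-value for chi-square, and comparing it with 0.025 is a literal use of Section 10.2. Even if one-sided testing is granted, the choice of test stays open, and Fisher raises the type II error for the 0.25% arm from the stated 15% to 21%.

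The choice can matter. With 16/45 responders against 5/35, the one-sided p-values are 0.016 (chi-square) and 0.028 (Fisher), and the two-sided ones are 0.032 and 0.041. Only the first is below 0.025. At the planned rates, the chance that one-sided chi-square rejects and two-sided Fisher does not is 12.4% for the 0.25% arm and 7.6% for the 0.5% arm.

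These numbers are right, and the omission is real. But they compare the reading that fits the text with the one furthest from it. The direction of H1 and H2 is fixed in advance, so the side is not open to choice once data are seen. What stays open is chi-square against Fisher, and ordinary practice on expected counts settles that. The difference between the two one-sided tests is 92.9 − 89.7 = 3.2 points for the 0.5% arm and 84.3 − 78.8 = 5.5 points for the 0.25% arm.

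It is also true that the matching reading controls the family-wise error at 0.05 one-sided. That level follows from hypotheses printed in the plan, so any reader can see it.

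**Conclusion.** The stated power is not an arithmetic error, and nothing shows that the correction was skipped. With H1 and H2 as written, 0.025 each and an uncorrected chi-square test, power is 92.9% and 84.3% exactly, or 93.1% and 85.0% by arcsine, against the stated 93% and 85%. This rests on the plan's own response rates and evaluable numbers, on reading the directional hypotheses as one-sided tests, and on chi-square being used when expected counts are adequate.

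The unstated side and the missing rule for choosing the test are gaps of detail that an analyst following Section 10.2 fills sensibly. Filling them this way leaves the sample size, the power figures and the primary conclusion as planned. The 88% and 76% would be the right figures only if two-sided primary tests were intended, and the text points the other way. No change is needed.

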10.4 Analysis Plan

10.4.1 Population for Analysis

All randomized infants who received study dose and non-randomized participants enrolled in the untreated control cohort will be included in the intent-to-treat population. The primary analysis will use the intent-to-treat population with treatment group determined by randomization assignment.

All infants enrolled and receiving at least one dose of timolol therapy will be included in the safety population and the safety analysis. All infants who had at least one interpretable PK sample will be included in the PK analysis.

10.4.2 Descriptive Statistics

Descriptive statistics such as number of observations, mean, median, standard deviation, standard error, minimum and maximum will be presented by groups for continuous variables (such as age, weight, etc.). Other descriptive statistics such as counts, proportions, and/or percentages will be presented by group to summarize discrete variables (such as race, sex, etc.). Participant disposition will be summarized, including the number of infants completed and early terminated from the study and the reasons for termination.

10.4.3 Demographic and Baseline Characteristics

Demographic and baseline characteristics will also be summarized. Variables include race, postnatal age, gestational age, sex, and selected clinical variables recorded prior to initiation of study drug. Study drug administration will be summarized in terms of number of days of dosing and reasons for final discontinuation of study drug.

10.4.4 Efficacy Analysis

Key efficacy endpoints are summarized in Section 10.1. Chi-square or Fisher's exact tests will be used to test response proportion hypotheses at study end. Response proportions will be further compared via odds ratio, difference in proportion, and confidence interval estimates.

Further adjusted analyses taking into account postnatal age, gestational age, and other baseline or demographic covariates of interest via logistic regression will be performed. Differences between studies used for the control data will be assessed.

As discussed in Section 10.1, randomized participants who switch to unmasked treatment with timolol maleate 0.5% GFS due to disease progression will be classified as treatment failures in the primary analysis. VAS scores following the switch to unmasked treatment will be analyzed as a secondary analysis. Both the VAS assessment of change from study baseline and change in VAS score from the time of treatment switching will be summarized in this secondary analysis. The duration of unmasked treatment will be summarized. Partial response of color or volume from the start of randomized treatment will be evaluated in participants who switch treatment using data collected after the treatment switch.

Additional secondary efficacy variables for analysis between randomized treatment arms include severity of the hemangioma, time to partial response, and quality of life measurement variables. Absolute change in overall severity will be measured via hemangioma dynamic complication scale from baseline to Day 180 within each treatment arm. Absolute change in quality of life will be measured via IH-QoL score scale from baseline to Day 180 within each treatment arm. Linear mixed effects modeling techniques will be used to analyze changes in the quantitative VAS scores, severity scale, or quality over time, and adjustments for demographic covariates of interest will be considered.

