Preliminary data on safety and outcomes of infants treated with topical timolol: The Hemangioma Investigator Group (HIG) conducted a retrospective, multicenter cohort study of topical timolol (applied directly to the hemangioma) solution for IH.³² This study included 738 infants from 9 pediatric dermatology and vascular anomalies centers, thereby demonstrating the wide off-label use of topical timolol for IH. The majority of infants were prescribed timolol in the outpatient setting and none of these received prolonged monitoring. During the active growth phase (0-3 months of age) 51% of infants showed improvement after 3 months of therapy and 82% after 6-9 months of therapy. AEs were rare, occurring in 3.4% of infants and there were no serious adverse events (SAEs).³² There were no serious cardiovascular adverse events.

Univariate and multivariate mixed-effects models showed that only initial IH thickness significantly predicted early improvement in size ($p = 0.0003$) and color ($p = 0.0001$ with IH <1 mm responding more quickly than IH 1-3 mm or >3 mm). The difference in response lost significance with longer duration of treatment, which may reflect natural involution of thicker lesions. While rebound growth with discontinuation of propranolol is well-recognized, optimal treatment duration for topical therapy to prevent rebound upon discontinuation has not been determined

Preliminary data collection on pharmacokinetics of topical timolol: Through the PTN study entitled “Pharmacokinetics of Understudied Drugs Administered to Children Per Standard of Care (NICHD-2011-POP01),” PK evaluation of topical timolol in premature infants with IH is ongoing. Preliminary serum levels in our PTN sponsored study range from 0.03-66.4 ng/ml with a median of 1 (standard deviation 13.0) ng/ml. None of the infants in this cohort had signs or symptoms of beta blockade or adverse events from timolol.

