6.3 Enrollment/Baseline

Research staff will obtain informed consent from the parent/guardian for all participants who satisfy eligibility criteria.

Once the informed consent has been obtained the following information will be recorded in the CRF:

1. Infant demographics, including birth weight and gestational age at birth and postnatal age.
2. Medical history (birth history and cardiac or pulmonary diagnoses)
3. Physical examination, including weight, height/length, baseline blood pressure, heart rate. Note, at the Baseline Visit, blood pressure* and heart rate must be at 1 hour and 2 hours after the first application of timolol.
4. Photographs and measurements of the IH. Collection of data on the clinical characteristics and measurement of width and thickness of the target hemangioma.
5. Adverse events following initial study-specific procedure (see Table 6-1)
6. Hemangioma Dynamic Complication Scale
7. Parental Hemangioma Quality of Life (QoL) screen
8. Concomitant Medications

* The preferred method of blood pressure collection is auscultation (i.e. manual), however, blood pressure may be collected via machine. Whichever method is used at visit #01 (baseline) should be used at all subsequent visits. Blood pressure measurements should include systolic and diastolic pressure measurements.

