7 STUDY PRODUCT DESCRIPTION

7.1 Dosage and Study Drug Information

Dosing scheme

Parents/guardians or hospital providers will topically apply 1 drop [approx. 0.05 ml of timolol maleate 0.5% GFS, which is 0.25 mg, or approximately 0.05 ml of timolol maleate 0.25% GFS, which is 0.125 mg] twice daily soon after feeding, to the surface of the hemangioma. The site will remain uncovered unless ulcerated or under the diaper, in which case a bandage will be applied when possible. Parents will record daily dosing in a log. Written instructions on how to apply study drug on the hemangioma will be provided to the parents at time of randomization and/or first study drug dispensing; the study site team (PI or designee) will show the parents how to apply the correct dose (i.e., drop) by applying the first treatment. Detailed instructions will be provided in the MOP. At each visit study drug bottles will be weighed to verify compliance. A discrepancy of >0.75g (+/-) between the expected bottle weight and the actual bottle weight at Visits 02 and 03 will be recorded as a protocol deviation. A bottle weight discrepancy of >1.5g (+/-) at Visits 05 and 07 will be recorded as a protocol deviation. Participants will not be early terminated because of a bottle weight discrepancy or participant non-compliance.

A deviation for participant non-compliance will be recorded if:

A participant has 12 or more missed doses per visit (previous 30 days of the treatment period)

A participant has 72 or more missed doses over the 6-month treatment period

A participant has 4 consecutive missed doses.

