10.4.5 PK Analysis

If possible, PK parameters will be estimated by the population PK approach using non-linear mixed effects modeling in NONMEM. The relationship between hemangioma characteristics (e.g. hemangioma thickness, timolol formulation, sex, application site, hemangioma surface area, ulceration, or occlusion) and study drug concentration will be estimated. Timolol data from the Pharmacokinetics of Understudied Drugs Administered to Children per Standard of Care study (PTN POP01) will be combined with the data obtained from this study for the exploratory PK analysis.

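### Section 10.4.4 names baseline lesion thickness in no efficacy model, although every infant has it measured and the protocol's own cohort found it the only significant predictor of early improvement

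*Combined protocol and SAP*

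**What the plan says.** Section 10.4.4 sets out three layers of efficacy analysis.

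- **Main tests of response.** As Section 10.2 puts it, "Hypotheses will be tested with chi-square or Fisher's exact tests". This covers the secondary dose hypothesis H3, whose alternative is: "The partial response proportion in the 0.25% arm is not equal to the partial response proportion in the 0.5% arm".
- **Adjusted response analysis.** "Further adjusted analyses taking into account postnatal age, gestational age, and other baseline or demographic covariates of interest via logistic regression will be performed".
- **Longitudinal models.** Linear mixed models for VAS scores, the severity scale and quality of life, for which "adjustments for demographic covariates of interest will be considered".

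Elsewhere the protocol treats lesion features as important:

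- Section 2.1 reports from the retrospective 738-infant cohort that "only initial IH thickness significantly predicted early improvement in size" (p = 0.0003; for color, p = 0.0001), with lesions under 1 mm responding faster than those of 1-3 mm or more than 3 mm. It adds that the difference was no longer significant with longer treatment.
- Section 6.3 requires at baseline, for all participants: "Collection of data on the clinical characteristics and measurement of width and thickness of the target hemangioma".
- Section 10.4.5 lists thickness as a factor for drug concentration, along with "application site, hemangioma surface area, ulceration, or occlusion".
- Section 5.3.2 stratifies randomization by site and age group (under 4 weeks vs 4 weeks or older). No lesion feature is a stratum.

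**The concern.** The comparison of 0.25% with 0.5% is the part of the efficacy evidence protected by randomization, because the untreated controls are external placebo patients and families who declined treatment (Section 4.1.1). With about 45 evaluable infants per arm, its precision matters most in the quantitative VAS analysis over Days 30, 60, 120 and 180.

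A baseline variable thought to predict response, and already on the case report form, would normally be named as a covariate in advance. The mixed-model sentence mentions demographic covariates only, which on its plain meaning excludes thickness. The logistic sentence admits thickness but does not name it, so the choice could be made after any imbalance between arms has been seen. At stake are some precision and the credibility that comes from fixing the model beforehand.

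**Working it through.** **1. The plan's own power figures (Section 10.3).** Inputs: control 0.15 (n = 35), 0.25% arm 0.45, 0.5% arm 0.50 (n = 45 each). The stated power is 93% and 85% after Bonferroni. The normal approximation is

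power = Φ[(d − 1.96·SE0)/SE1], with SE0 pooled and SE1 unpooled.

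- 0.5% vs control: (0.35 − 1.96 × 0.1073)/0.0959 = 1.46, giving 92.7%.
- 0.25% vs control: (0.30 − 1.96 × 0.1050)/0.0956 = 0.98, giving 83.8%.
- Exact enumeration of the chi-square test gives 92.9% and 84.3%.

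The figures reproduce to within about one point at one-sided 0.025. The documents give no power for H3.

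**2. H3 at the planned rates (0.45 vs 0.50, 45 per arm, two-sided 0.05).** SE0 = √(2 × 0.475 × 0.525/45) = 0.1053 and SE1 = √((0.2475 + 0.25)/45) = 0.1051. Then (0.05 − 1.96 × 0.1053)/0.1051 = −1.49, so power is about 6.9%. Exact enumeration gives 7.0% (chi-square) and 4.5% (Fisher).

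**3. Effect of adding thickness to the logistic comparison.** This is a simulation of likelihood-ratio tests with 45 per arm and 1,500 runs. Two inputs are assumed, because the documents do not give them: half the lesions fall in the thicker class, and the thickness odds ratio ranges from 1 to 8.

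| Thickness odds ratio | 0.45 vs 0.50: unadjusted / adjusted | No difference (0.45 both): unadjusted / adjusted |
|---|---|---|
| 1 | 6.5% / 7.7% | 4.5% / 5.0% |
| 2 | 7.7% / 8.3% | 3.9% / 4.9% |
| 4 | 7.1% / 7.9% | 4.9% / 6.3% |
| 8 | 7.5% / 9.1% | 5.7% / 5.9% |

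The simulation error is about 0.6 to 0.7 points. A gap of about one point appears even at odds ratio 1, where thickness has no effect, so the differences in the power column are not evidence of a useful gain.

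**4. Effect in the VAS model.** For a continuous outcome at one visit, a covariate that explains a share R² of the variance is worth 1/(1 − R²) − 1 extra infants. The documents give no R². Assumed values of 0.05, 0.10, 0.20 and 0.30 give 5%, 11%, 25% and 43%. A covariate that explains nothing costs roughly 1/88 to 2/88 of the information (one or two of about 88 residual degrees of freedom), or 1 to 2%.

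**5. Does eligibility remove the factor?** No. Section 5.2.1 admits lesions under 2 mm, which spans the cohort's class under 1 mm and part of its 1-3 mm class. If half the lesions were thicker (assumed), the between-arm difference in that share would have a standard deviation of √(2 × 0.25/45) = 0.105, about 10 percentage points.

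**6. Lesion area.** Eligibility sets an upper limit in cm² and Section 10.4.5 uses surface area. The measurements listed in Sections 6.3, 6.4.1 and 6.4.2 and in the lesion-exam footnote to Table 6-1 are width and thickness. The documents do not say how area is obtained.

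**The case against.** The case for leaving the plan alone has real force.

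- **The logistic model is open.** Its wording admits any baseline covariate, so thickness is not excluded there. This stands: for that model the gap is only that the covariate is not named.
- **The thickness evidence concerns early improvement.** It comes from a retrospective cohort and lost significance with longer treatment, whereas H3 is read at Day 180. Restricting entry to lesions under 2 mm narrows the range further. This stands, and it limits the expected benefit mainly to the earlier visits.
- **Validity is not in question.** Randomization balances thickness on average, and the error rate of the unadjusted test already allows for chance imbalance. This stands.
- **Demographic may be loose wording.** Section 10.4.3 groups demographic variables with selected clinical variables recorded before treatment. Even there, however, the clinical variables are a separate item, so the mixed-model sentence does not clearly reach thickness.

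A reader might also infer something stronger from the dosing text, "Parents/guardians or hospital providers will topically apply 1 drop", which holds whatever the lesion area. Comparing a circular lesion 0.5 cm across (0.196 cm²) with one of 10 cm² gives a 10/0.196 = 51-fold range in drug per cm², against a 2-fold contrast between arms. The documents do not support building the point on that. The figure compares eligibility extremes and depends on an assumed shape (40-fold for a square, 102-fold for a 0.5 × 0.25 cm ellipse). The same range applies in both randomized arms, so it does not confound the contrast. The documents also report no effect of area on response.

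**Conclusion.** The point holds as a matter of prespecification and modest precision. Section 10.4.4 restricts the mixed models to demographic covariates and names no lesion feature in the logistic model. The one predictor singled out by the cited cohort is therefore unused for efficacy, although it is collected in every infant and used for PK.

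The size depends on the analysis:

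- In the VAS model the gain equals 5 to 43% more infants over the assumed R² range of 0.05 to 0.30. The low end, or less, is more plausible at Day 180 because the effect faded.
- For H3 at the planned 45% vs 50%, power is about 7 to 9% either way.

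A reader might conclude that the dose comparison is biased without thickness, or that adjustment would rescue H3. The documents and the calculations support neither. The case for thickness rests on a retrospective finding; the case for area rests only on the protocol's own use of it for eligibility and PK.

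**What to change.** In Section 10.4.4:

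1. Prespecify baseline lesion thickness (continuous, or under 1 mm vs 1 to under 2 mm) and the age-group randomization stratum as fixed covariates in the longitudinal VAS mixed model and in the adjusted logistic comparison of 0.25% vs 0.5%.
2. Add log baseline lesion area as a further covariate where it can be derived, and state how. If it is to come from caliper measurements, add the longest dimension to the listed measurements in Sections 6.3, 6.4.1 and 6.4.2 and Table 6-1. If it is to come from the photographs, say so.
3. Keep the unadjusted chi-square or Fisher test of H3 as planned.

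The cost is a few lines of text, possibly one data field, and one or two degrees of freedom (about 1 to 2% of the information if the covariates prove useless). Sample size, treatment and the primary tests do not change.
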